10.1.2 Analysis Sets

Safety Analysis Set

The analysis of all endpoints, unless noted otherwise, will be conducted on the Safety Analysis Set defined as all subjects that are enrolled and receive at least one administration of AMG 596.

RANO Evaluable Analysis Set

The RANO Evaluable Analysis Set includes all subjects that are enrolled and receive at least one administration of AMG 596 with measurable disease at enrollment per RANO.

DLT Evaluable Analysis Set

- The DLT Evaluable Analysis Set includes subjects who are DLT-evaluable and will be used to summarize incidence of dose limiting toxicity (DLT) (see [Section 3.3](#) for definition of DLT-evaluable).

10.1.3 Covariates and Subgroups

Due to the small sample size, the impact of baseline characteristics on study outcomes will not be explored, and no subgroup analyses will be performed.

Approved

10.2 Sample Size Considerations

It is anticipated that up to 190 subjects will be enrolled in the study. It is anticipated that up to 100 subjects will be enrolled to Arm 1 in this study and up to 90 subjects will be enrolled to Arm 2 in this study.

For Group 1 (recurrent disease), the following are the planned sample sizes.

- In dose escalation, up to 45 DLT-evaluable subjects will be enrolled to monotherapy Arm 1 and up to 30 DLT-evaluable subjects to combination Arm 2
- In dose expansion, up to 15 subjects will be enrolled to monotherapy Arm 1 and up to 15 subjects to combination Arm 2.

For Group 2 (maintenance setting), the following are the planned sample sizes.

- In dose escalation, up to 15 DLT-evaluable subjects will be enrolled to monotherapy Arm 1 and up to 20 DLT-evaluable subjects to combination Arm 2
- In dose expansion, up to 25 subjects will be enrolled to monotherapy Arm 1 and up to 25 subjects to combination Arm 2

The sample sizes in dose escalation are based on practical considerations and it is consistent with conventional oncology studies with the objective to identify the RP2D/MTD. With 2 subjects per cohort, there is a 19-56% probability of observing at least one DLT for a cohort if the true DLT rate is 10-33% and with 6 subjects per cohort, the probability is 47-91%.

For Group 1 (recurrent disease) in each respective arm (monotherapy and combination), the respective sample sizes of the dose expansion cohorts are based on practical considerations. With 21 subjects treated at the RP2D/MTD (6 from dose escalation and 15 from dose expansion) in an arm, there is a 66% probability of observing an adverse event with 5% incidence rate. For an ORR of 20%, the probability of observing the OR in at least 4 subjects would be 63%. The estimated ORR and exact 80% CI for 4 responses is 19% and 9%-35% respectively.

For Group 2 (maintenance setting) in each respective arm (monotherapy and combination), the sample sizes in the respective dose expansion arm are based on a Bayesian predictive probability design (Lee, 2008). For both arms, the ORR of interest is 20% or higher while an ORR of 5% or less is considered insufficient antitumor-activity. The maximum sample size per arm is 31 subjects (6 from dose escalation and 25 from dose expansion). Futility will be assessed initially after treating 10 subjects for at least 6 months and continuously for each additional subject afterwards. If ORR is lower than

5%, enrollment may be terminated due to futility. The guidelines for early termination due to futility are as follows:

| Number of Treated Subjects | Futility Termination Guideline |
|----------------------------|--------------------------------|
| 10 | 0 responders |
| 19 | 1 or fewer responders |
| 26 | 2 or fewer responders |
| 31 | 3 or fewer responders |

With this design, the probability of accepting the treatment is 0.05 (type I error) when ORR=5% and 0.8 (power) when ORR=20%. If the ORR is 5%, the probability of stopping the trial early at the interim with 10 evaluable subjects for futility is 60% and the expected additional subjects to be assessed in dose expansion is 9.6.

During dose expansion and separately for the monotherapy arm (combining data from Groups 1 and 2) and for the combination arm (combining data from Groups 1 and 2), Amgen will conduct evaluations of the ongoing grade 4 or higher treatment-related adverse event rate to assess if the threshold for possible early trial termination has been reached. If this threshold is met, enrollment to dose expansion will be halted pending review of safety data by the DLRT. After receiving the DLRT recommendation, Amgen will choose to take one of the following actions.

- 1) Terminate the trial
- 2) Amend the protocol to potentially improve the benefit/risk for subjects (eg, increase safety monitoring, modify dose/schedule, mandate premedication)
- 3) Continue dose expansion without any changes

The stopping rules use a Bayesian approach proposed by Thall, Simon, and Estey (1995) to terminate the study if the posterior probability that the grade 4 or higher treatment-related adverse event rate is greater than 20% is > 80%. The stopping boundaries assume a prior distribution of Beta (0.40, 1.60) are presented in [Table 19](#) and the operating characteristics with pre-specified batch size of 10 new subjects per batch are presented in [Table 20](#). Subjects included in a batch may come from different study groups. The evaluations could occur more frequently if necessary to address emerging safety concerns. The operating characteristics in [Table 19](#) provide the probability of stopping the trial early for given hypothetical true rate of grade 4 or higher treatment-related adverse events, whereas the stopping criteria in [Table 20](#) are based

Approved

on situations where the empirical evidence would result in a posterior probability of $\geq 80\%$ that the true grade 4 or higher treatment-related adverse event rate is $\geq 20\%$.

Table 19. Stopping Boundary for Dose Expansion

| Number of subjects | Hold enrollment if observing this many grade 4 or higher treatment-related adverse events |
|--------------------|---|
| 10 | ≥ 4 |
| 20 | ≥ 6 |
| 30 | ≥ 9 |
| 40 | Study Complete |

Table 20. Operating Characteristics with Batch Size of 10 Subjects

| True grade 4 or higher treatment-related adverse event rate | Probability of early stopping of dose expansion | Average dose expansion sample size |
|---|---|------------------------------------|
| 0.10 | 2.0% | 39.5 |
| 0.15 | 9.7% | 37.6 |
| 0.20 | 25.8% | 33.9 |
| 0.25 | 47.7% | 28.8 |
| 0.30 | 69.2% | 23.4 |

10.3 Adaptive Design

During dose escalation for both Arm 1 and Arm 2, a two-parameter Bayesian logistic regression model (BLRM, [Neuenschwander et al, 2008](#)) is used to guide dose exploration. The MTD target Toxicity Probability Interval (TPI) for DLT is (0.20, 0.33] and TPIs of (0.33, 0.60] and (0.60, 1.00] are defined as excessive and unacceptable, respectively. The design seeks to identify a dose most likely to have a DLT rate in the target TPI, but with overdose control that limits the possibility the dose has an excessive or unacceptable DLT rate ([Babb et al, 1998](#)). The DLT endpoint at dose level d_i is assumed to follow a Bernoulli distribution with probability p_i where the logit of p_i increases linearly with the log of the standardized dose in the following 2-parameter logistic model:

$$\log [p_i / (1-p_i)] = \text{logit}(p_i) = \log[a] + \exp(\log[b]) \log (d_i / d_{\text{ref}})$$

where a and b are random variables and d_{ref} is one of the planned doses selected as the reference dose.

Approved

For both Arm 1 and Arm 2, a bi-variate normal prior distribution (Neuenschwander, Branson and Gsponer; 2008) is used to select for $\theta = (\log a, \log b)$ where the probability that the true DLT rate is ≤ 0.40 at the lowest monotherapy planned dose (████ μg/day) is 0.90 and the probability the true DLT rate is ≤ 0.05 at the reference dose (████ μg/day) is 0.05. These values were selected such that π is 0.05 for the starting dose and 0.25 for the reference dose. Model sensitivity to the prior will also be investigated and in particular the BLRM will be examined using a prior having a lower reference dose (eg, █████ μg/day) and using a prior having a higher reference dose (eg, █████ μg/day).

10.4 Planned Analyses

10.4.1 Interim Analyses

Arm 1

In dose escalation, the DLRT will review the safety data after each cohort and make a decision on the next dose level to be explored for the estimate of RP2D/MTD based on a BLRM design. The RP2D/MTD will be established separately for Group 1 (recurrent disease) and Group 2 (maintenance setting) subjects. The interim analysis will include the establishment of RP2D/MTD and the estimate of ORR.

- The first interim of safety data analysis in Part 1 dose escalation will happen at the earlier of
 - When 15 subjects enrolled and completed DLT observation or
 - Completion of dose escalation of Group 1. Efficacy data will also be analyzed for subjects who have had at least one imaging evaluation after start of treatment or have dropped out before that.

Interim safety analyses during dose expansion will occur once 1) 5 subjects with recurrent disease have been enrolled and 2) after enrollment of 10 subjects with maintenance setting. The BLRM will estimate the RP2D/MTD using available data from dose escalation and dose expansion. Based on this revised RP2D/MTD estimate and reviewing all available safety data, the dose level for dose expansion may be revised.

In Part 2 dose expansion, the ORR will be evaluated after treating n=10 Group 2 subjects for at least 6 months. The futility will be assessed initially for N=10 and continuously afterwards using a Bayesian predictive probability design. Enrollment may be terminated if insufficient antitumor-activity is observed.

Arm 2

In dose escalation, the DLRT will review the safety data after each cohort and make a decision on the next dose level to be explored for the estimate of RP2D/MTD based on a

BLRM design. The RP2D/MTD will be established separately for Group 1 (recurrent disease) and Group 2 (maintenance setting) subjects.

Interim safety analyses during dose expansion will occur once 1) 5 subjects with recurrent disease have been enrolled and 2) after enrollment of 10 subjects with maintenance setting. The BLRM will estimate the RP2D/MTD using available data from dose escalation and dose expansion. Based on this revised RP2D/MTD estimate and reviewing all available safety data, the dose level for dose expansion may be revised.

In Part 2 dose expansion, the ORR will be evaluated after treating n=10 Group 2 subjects for at least 6 months. The futility will be assessed initially for N=10 and continuously afterwards using a Bayesian predictive probability design. Enrollment may be terminated if insufficient antitumor-activity is observed.

10.4.2 Dose Level Review Team (DLRT)

Dose level review meetings (DLRMs) will be held to review data, monitor safety, and make dose escalation/change decisions. The review team will be composed of the investigators, Amgen Medical Monitor/ Early Development Leader, Amgen Global Safety Officer or designated safety scientist, Amgen Clinical Research Study Manager and Biostatistics representative. Additional members may be added as needed (eg, Biomarker Scientist, PK Scientist). A quorum, defined as > 50% of the participating investigators or their qualified designee [ie, sub-PI or research nurse or study coordinator possessing hard copy documentation (eg, email) of the PI's vote regarding the dose level review], must be in attendance for DLRM. The following DLRT members are responsible for dosing decisions: investigators, Amgen Medical Monitor, Early Development Leader, and Amgen Global Safety Officer. The DLRM will be rescheduled if a quorum is not reached.

The DLRT members are responsible for dosing decisions, which may include escalation to the next planned dose, escalation to an intermediate dose (a dose lower than the next planned dose), de-escalation to a lower dose; continuation, delay, or termination of dosing; or repetition or expansion of a cohort or start of step-dosing. All available study data, including demographics, investigational product administration, medical history, concomitant medications, adverse events, ECGs, vital signs, laboratory results, and PK/PD information will be reviewed. In addition to DLTs, all \geq grade 3 toxicities not meeting DLT criteria (including hematologic) will be reviewed by the team and can be considered in the DLRT's decisions. Data to be reviewed will be queried.

10.4.3 Primary Analysis

A primary analysis will be performed for each group separately when target enrollment in Part 1 and Part 2 is complete and each subject either completes 6 months on study or withdraws from the study.

10.4.4 Final Analysis

A final analysis for each group is planned after all subjects in each group have ended the study (parts 1 and 2).

10.5 Planned Methods of Analysis

10.5.1 General Considerations

The analyses described below will be reported separately for subjects enrolled to Arm 1 and for subjects enrolled to Arm 2. Unless otherwise specified, the analyses will be done using the Safety Analysis Set.

Descriptive statistics will be provided for selected demographics, safety, PK, PD, efficacy and biomarker data by dose, dose schedule, and time as appropriate. Descriptive statistics on continuous data will include means, medians, standard deviations and ranges, while categorical data will be summarized using frequency counts and percentages. ORR will be presented with 80% Clopper-Pearson exact CI using the RANO Evaluable Analysis Set. PFS will be summarized using Kaplan-Meier method. Graphical summaries of the data may also be presented.

10.5.2 Primary Endpoint(s)

Dose Limiting Toxicities (DLT)

The DLT endpoint will be analyzed using the DLT Evaluable Analysis Set. The probability of each TPI and of a DLT from the BLRM will be summarized by dose and group along with the estimated dose-toxicity curve. Subject incidence of DLT by dose level and group will be summarized.

Adverse Events

Subject incidence of all treatment-emergent adverse events will be tabulated by system organ class and preferred term. The number and percentage of subjects reporting adverse events will be evaluated overall and by dose level and will also be tabulated by relationship to study drug.

Tables of fatal adverse events, serious adverse events, adverse events leading to withdrawal from investigational product or other protocol-required therapies, and significant treatment-emergent adverse events will also be provided.

Disease-Related Event (DREs)

Safety endpoints (eg, mortality and morbidity) that are study endpoints are reported on an eCRF. A negatively adjudicated safety endpoint will be reported to the investigator and treated by Amgen as appropriate. This could include no action, or a report on the eCRF as a Disease-Related event, an adverse event, or a serious adverse event.

Clinical Laboratory Tests

Clinical chemistry, hematology, and urinalysis data will be listed and reviewed for each subject. Values outside the normal laboratory reference ranges will be flagged as high or low on the listings. Depending on the size and scope of changes in laboratory data, summaries of laboratory data over time and/or changes from baseline over time may be provided. Tables of maximum shifts from baseline for selected laboratory values may also be provided.

Vital Signs

Vital signs data will be listed and reviewed for each subject. Depending on the size and scope of changes, summaries of vital signs data over time and/or changes from baseline over time may be provided.

Electrocardiograms

Summaries over time and/or changes from baseline over time will be provided for all ECG parameters.

Subjects' maximum change from baseline in QTc will be categorized and the number and percentage of subjects in each group will be summarized.

Subjects' maximum post baseline values will also be categorized and the number and percentage of subjects in each group will be summarized.

All on-study ECG data will be listed and select parameters of interest may be plotted.

10.5.3 Secondary Endpoint(s)

For all subjects in part 1 and part 2 listings will be produced indicating the time to progression, time to response, and duration of response.

Using the RANO Evaluable Analysis Set, an exact 80% CI will be estimated for the OR rate for all subjects in part 2 and those in part 1 treated at RP2D/MTD for each group. Among these subjects, the proportion of subjects that are progression free at 6 months and 12 months with corresponding exact 80% CI will be calculated. A Kaplan-Meier

Approved

[figure not shown]
curve may be presented for time to progression with estimates for rates and 80% CI at selected weeks.

Pharmacokinetic Analyses

The serum PK parameters of AMG 596 as monotherapy or in combination therapy with AMG 404 including, but not limited to, average C_{ss} , area under the concentration-time curve (AUC), clearance, volume of distribution, half-life ($t_{1/2}$), [REDACTED] and serum PK parameters of AMG 404 including, but not limited to, C_{max} , t_{max} , and AUC will be estimated using non-compartmental methods and summarized by dose level using means, standard deviations, medians, minimums, and maximums.

[REDACTED] Summary statistics will be computed for each sampling time and parameter as appropriate.

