1.2 Secondary

The secondary objectives of this study are to:

- Evaluate the pharmacokinetics (PK) of AMG 596 in serum when administered by cIV infusion either in monotherapy or in combination with AMG 404
- Evaluate the pharmacokinetics (PK) of AMG 404 in serum when administered by short term infusion in combination with AMG 596
- Evaluate the clinical benefit of AMG 596 monotherapy or AMG 596 in combination with AMG 404 as determined by objective response rate (ORR) per modified Response Assessment in Neuro-Oncology Criteria (RANO) ([Okada et al., 2015](#)) in subjects with EGFRvIII-positive glioblastoma or malignant glioma in the recurrent and in the maintenance setting
- Evaluate progression free survival rate at 6 and 12 months after initiation of treatment for any Part, Arm and Group of the study

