4. SUBJECT ELIGIBILITY

4.1 Inclusion Criteria

101. Subject has provided written informed consent prior to initiation of any study-specific activities/procedures
102. Male or female, of at least 18 years of age

103. Eastern Cooperative Oncology Group (ECOG, [Appendix F](#)) Performance Status of ≤ 1
104. Life expectancy of at least 3 months, in the opinion of the investigator.
105. Must have pathologically documented, and definitively diagnosed World Health Organization (WHO) grade 4, glioblastoma or lower grade malignant gliomas with EGFRvIII positive tumor
106. Must have recurrent disease confirmed by MRI (Group 1) or completed SoC therapy such as surgery with adjuvant radiochemotherapy with or without maintenance temozolomide according to local standards for newly diagnosed disease (Group 2)
107. Group 1 subjects must have ≥ 1 index lesion by modified RANO criteria ([Appendix D](#)), exemption: non-measurable disease is allowed for subjects with re-surgery (surgery for recurrent disease) before start of screening; Group 2 subjects must have radiographically measurable disease or non-measurable disease by modified RANO criteria or both at the time of enrollment are allowed:
 - Bidimensionally measurable, contrast-enhancing lesions with clearly defined margins by MRI with perpendicular diameters of at least 10 mm x 10 mm and noted in more than one imaging slice
 - Imaging must be performed within 14 days of enrollment. Subject can be on stable dose steroid medication (systemic corticosteroid doses of ≤ 2 mg of dexamethasone (or equivalent) per day after consultation with Sponsor) for at least 5 days immediately before and during imaging study
108. Confirmed EGFRvIII positivity from pre-screening or confirmation at time of study enrollment required if prior treatment included EGFRvIII – or amplified EGFR- targeted therapy (one test sufficient, please refer to [Section 7.2.1](#))
109. Archived tumor tissue from initial diagnosis or subsequent relapse for submission to central review
110. Hematological function as follows:
 - Absolute neutrophil count (ANC) $> 1500/\text{mm}^3$ ($1.5 \times 10^9/\text{L}$)
 - Platelet count $> 100,000/\text{mm}^3$ ($100 \times 10^9/\text{L}$)
 - White blood cell (WBC) count $> 3 \times 10^9/\text{L}$
 - Hemoglobin > 9.0 g/dL

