9.5 Efficacy Analyses

Unless otherwise specified, all subjects that are enrolled and receive at least one administration of AMG 596 at the MTD (the efficacy analysis set) will be included in the analysis of the secondary efficacy endpoints.

The following methods will be used with Kaplan-Meier analyses of efficacy endpoints.

- Estimation of the median and CI will use the Brookmeyer and Crowley (1982) method
- Landmark estimates (eg, 6 month PFS) will be estimated using the Kaplan-Meier curve and CI using Greenwood's formula to estimate the standard error (see [Kalbfleisch J.D. and Prentice R.L. \(1980\)](#))

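### As most naturally read, the protocol limits the 6- and 12-month progression-free rates to subjects with measurable disease, which the endpoint does not need and eligibility does not require, and the SAP uses a different set

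*Protocol*

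**What the plan says.** - **Protocol 10.5.3** first deals with response: "Using the RANO Evaluable Analysis Set, an exact 80% CI will be estimated for the OR rate for all subjects in part 2", together with Part 1 subjects treated at the RP2D/MTD, for each group. The next sentence reads: "Among these subjects, the proportion of subjects that are progression free at 6 months and 12 months", with an exact 80% CI.
- **Protocol 10.1.2** defines the RANO Evaluable set as "all subjects that are enrolled and receive at least one administration of AMG 596 with measurable disease at enrollment per RANO".
- **Protocol 10.5.1** sets a general default, "Unless otherwise specified, the analyses will be done using the Safety Analysis Set". It names the RANO set for ORR and then mentions a Kaplan-Meier summary of PFS without naming a set.
- **SAP 9.5** has its own default for secondary efficacy endpoints: "Unless otherwise specified, all subjects that are enrolled and receive at least one administration of AMG 596 at the MTD". SAP 9.5.1 assigns the RANO set to ORR and response categories and names no set for PFS, so the default applies. SAP section 6 puts no measurability condition on that set.
- **Protocol 1.2** gives the objective: "Evaluate progression free survival rate at 6 and 12 months after initiation of treatment for any Part, Arm and Group of the study".
- **Protocol 4.1, criterion 107**: "Group 2 subjects must have radiographically measurable disease or non-measurable disease by modified RANO criteria or both at the time of enrollment". It also exempts Group 1 subjects from the index-lesion requirement after surgery for recurrence.

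**The concern.** Measurable disease is a sensible condition for response, because a partial response needs a baseline lesion area that can shrink by half. Progression-free status has no such need. SAP section 5 counts radiological progression or death as a PFS event. The modified RANO table allows progression through new lesions or substantially worsened T2/FLAIR. A treated subject without a measurable lesion can therefore have the event and be followed for it.

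If these subjects are left out, the maintenance-group rate describes only those with measurable residual tumor, not the population that criterion 107 enrolls. The protocol and the SAP would then report a rate under the same name from different subjects. If this is left open until results are known, the denominator becomes a post hoc choice.

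**Working it through.** **Which set applies to the 6- and 12-month rates**

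| Source | Set | Measurable disease required |
|---|---|---|
| Protocol 10.5.3, natural reading | RANO Evaluable; Part 2 plus Part 1 at RP2D/MTD | Yes |
| Protocol 10.5.3, alternative reading | Part 2 plus Part 1 at RP2D/MTD | No |
| SAP 9.5 and 9.5.1 | Efficacy set: treated at the MTD | No |

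The estimator differs as well. The protocol gives an exact binomial proportion, and the SAP gives a Kaplan-Meier landmark with a Greenwood standard error.

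**Check of the interval method.** Protocol 10.2 states that 4 responses in 21 give 19% with an exact 80% CI of 9%-35%. Clopper-Pearson at 80% for 4/21 = 19.0% gives 8.6%-34.5%, which agrees.

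**Loss of precision in Group 2.** The planned maximum per arm at the RP2D/MTD is 6 + 25 = 31 (protocol 10.2). Let f be the share with only non-measurable disease. The documents do not give f; 30% and 50% are assumed here.

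n = 31 × (1 − f)

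- f = 0: n = 31. At 15/31 = 48.4% the interval is 35.7%-61.3%, width 0.256.
- f = 0.30: 31 × 0.70 = 21.7, about 22. At 11/22 = 50% the interval is 34.6%-65.4%, width 0.308.
- f = 0.50: 31 × 0.50 = 15.5, about 16. At 8/16 = 50% the interval is 31.8%-68.2%, width 0.364.

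**Shift in the rate.** Let p_m and p_n be the progression-free rates with measurable and with only non-measurable disease. The all-treated rate is (1 − f)·p_m + f·p_n, and the RANO-set rate is p_m, so

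RANO-set rate − all-treated rate = f × (p_m − p_n)

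Neither rate is in the documents. Illustrations:

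- p_m = p_n: shift 0 for any f.
- p_m = 50%, p_n = 65%: 0.30 × (−15) = −4.5 points; 0.50 × (−15) = −7.5 points.
- p_m = 65%, p_n = 50%: +4.5 and +7.5 points.

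**The case against.** **The alternative reading.** The RANO phrase stands at the head of the response-rate sentence, and the nearest antecedent of the linking phrase is the list of Part 2 and Part 1 RP2D/MTD subjects. The summary of changes shows that Amendment 5 added the RANO phrase to the response-rate sentence, and protocol 10.5.1 attaches the set to ORR only. The protocol may therefore already intend a rate without the restriction. This stands as a possible reading. It does not make the text clear, and the natural reading remains the restricted one.

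**Appendix D.** Both documents' Appendix D says that inclusion requires at least one measurable lesion. If that were enforced, nobody would be dropped. It conflicts with criterion 107, however, and the SAP's own change history says the RANO set was added because eligibility admits inevaluable scans. The two protocol passages need reconciling.

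**Timing.** The SAP is dated May 2019 and cites the protocol of 05 July 2017; Amendment 5 is dated 29 July 2019. A reader might infer that the SAP section 10 statement of no changes is false. The dates do not support that, because the SAP could not describe text written after it. The mismatch still has to be resolved when the SAP is updated.

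**Importance.** PFS here is secondary and descriptive, with no threshold or decision rule; the Group 2 stopping rules use ORR. Time to progression is listed for all subjects in both parts, so data are not lost from the report. This limits the weight of the point but does not remove it.

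**Conclusion.** The point holds as a defect of population definition that should be corrected. On its natural reading, protocol 10.5.3 removes eligible subjects from a secondary endpoint that does not need measurable disease, in Group 2 and among re-operated Group 1 subjects, and the SAP does not apply that restriction. With an assumed 30-50% non-measurable, n falls from 31 to about 22-16 per Group 2 arm, and the 80% CI width near a 50% rate rises from 0.26 to 0.31-0.36. Some loss of denominator occurs whenever such a subject is treated in the stated dose stratum.

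Three stronger readings are not supported:

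- **Three populations prescribed for these rates.** Only two sets are named. The Safety-set default in 10.5.1 yields to a specific statement, and 10.5.3 makes one.
- **A biased rate.** The plan gives neither the non-measurable share nor any rate by measurability, so the shift may be zero, negative or positive.
- **Clinical decline as a PFS event in every subject.** The SAP definition counts radiological progression or death only. The argument does not depend on clinical decline.

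**What to change.** In protocol 10.5.3 and SAP 9.5.1:

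1. State that PFS and the 6- and 12-month rates use all treated subjects in Part 2 plus Part 1 subjects treated at the RP2D/MTD, by arm and group, regardless of measurable disease. The stratum should follow treatment received, in line with protocol 10.5.3 and SAP section 6.
2. Keep the RANO Evaluable set for ORR and response categories.
3. Report the rates for the remaining Part 1 subjects descriptively, so that the objective in protocol 1.2 is met for every part, arm and group.
4. Reconcile Appendix D with criterion 107.

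The cost is wording in a few sections and no new data. The downside is that the progression-free rate no longer shares the ORR denominator, so tables should show both denominators.
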